#### **9.4 Demographics and Baseline Characteristics**

Demographics and baseline characteristics will be summarized for the safety population, the PK half-dose population, the PK completer population, the randomized population, the efficacy population, and the continued access population. The summaries of data will include numbers and percentages for categorical variables and mean, standard deviation, median, minimum, and maximum for continuous variables. Tables for the randomized population and the efficacy population will be by randomized treatment group (Xyrem or Xyrem placebo) and overall. The randomized population tables will include a comparison of the treatment groups, with categorical variables analyzed using a chi-square test and continuous variables analyzed using a one-way analysis of variance (ANOVA) model with treatment as the only factor.

#### **9.5 Handling of Dropouts and Missing Data**

The following methods will be used to handle missing efficacy data and data from subjects who discontinue early in the Double-Blind Treatment Period. The weekly number of cataplexy attacks will be computed as the average from days with non-missing data, multiplied by 7. School attendance will be calculated as the number of missed days, multiplied by 100, divided by the actual number of school days (not including holidays) up to the point of Part 1 early termination or Double-Blind Treatment Period completion. The last post Stable-Dose Period assessment of all other measures will be used as the end of the Double-Blind Treatment Period assessment.

Xyrem® (sodium oxybate) oral solution  
Clinical Study Protocol: 13-005 Amendment 5

Jazz Pharmaceuticals.

---

## 9.6 Efficacy Endpoints

All efficacy assessments will be comparisons of the measurement made during, or at the end of, the last 2 weeks of the Stable-Dose Period compared with the 2 weeks of Double-Blind Treatment Period.

Primary endpoint:

1. Change in weekly number of cataplexy attacks

Key secondary endpoints:

2. CGIc for cataplexy severity
3. Change in the ESS (CHAD) score

Other secondary endpoints:

4. CGIc for narcolepsy overall
5. Change in Quality of Life (QoL) (SF-10)

Exploratory endpoints:

6. Change in weekly school attendance (if enrollment overlaps with school attendance period)
7. PGIC for narcolepsy overall

### 9.6.1 Statistical Analysis

#### To address Primary Objective 1 and Secondary Objective 1:

A tiered approach was planned to control the Type 1 family-wise error rate at the 0.05 significance level with all tests being two-sided for testing of the primary and secondary efficacy endpoints.

Due to the positive primary efficacy results from the pre-specified interim analyses (described in [Section 9.8](#)), the DSMB recommended to stop the Double-Blind Randomized-Withdrawal Period. Tiered testing on secondary endpoints, as defined below, will be conducted with a significance level of 0.05, with all tests being two-sided.

Tier 1: Primary endpoint

1. Change in weekly number of cataplexy attacks from the last 2 weeks of the Stable-Dose Period to the 2 weeks of the Double-Blind Treatment Period.

The primary endpoint demonstrated efficacy at the interim analysis with a significance level <0.005. Testing will continue with Tier 2.

Tier 2: Key secondary endpoint #2

2. CGIc for cataplexy severity from the end of the Stable-Dose Period to the end of the Double-Blind Treatment Period

The testing of this endpoint will be conducted at the 0.05 significance level. If Xyrem is significantly better than placebo at this level, Tier 3 tests will be conducted.

Tier 3: Key secondary endpoint #3

Xyrem® (sodium oxybate) oral solution  
Clinical Study Protocol: 13-005 Amendment 5

Jazz Pharmaceuticals.

3. Change in the ESS (CHAD) score from the end of the Stable-Dose Period to the end of Double-Blind Treatment Period

The testing of this endpoint will be conducted at the 0.05 significance level. If Xyrem is significantly better than placebo at this level, Tier 4 tests will be conducted.

Tier 4: Other secondary endpoints #4

4. CGIc for narcolepsy overall from the end of the Stable-Dose Period to the end of the Double-Blind Treatment Period

The testing of this endpoint will be conducted at the 0.05 significance level. If Xyrem is significantly better than placebo at this level, Tier 5 tests will be conducted.

Tier 5: Other secondary endpoint #5

5. Change in QoL (SF-10) from the end of the Stable-Dose Period to the end of the Double-Blind Treatment Period

The testing of this endpoint will be conducted at the 0.05 significance level.

Exploratory efficacy endpoints will be tested without multiplicity adjustments. For these parameters, nominal p-value will be reported.

Non-categorical efficacy parameters will be analyzed by non-parametric analysis of covariance (ANCOVA). Ordinal categorical parameters, including CGIc and PGIC, will be analyzed using Cochran–Mantel–Haenszel (CMH) tests for row mean score difference.

Efficacy data in the open-label phase will be summarized by visit.

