## 1.1 Background and Rationale

This study is being conducted under the US Food and Drug Administration's (FDA) pediatric Written Request.

On February 24, 2016, the Data and Safety Monitoring Board (DSMB) for this study reviewed the results from a pre-planned interim analysis of the primary efficacy results based on 35 subjects having completed or discontinued from the Double-blind Randomized Withdrawal Period of the protocol. The result of this analysis demonstrated positive efficacy on the primary endpoint, the change in weekly number of cataplexy attacks from the last 2 weeks of the Stable-Dose Period to the 2 weeks of the Double-Blind Treatment Period at a significance level of  $p < 0.005$ . Based on this analysis, the DSMB recommended that the placebo treatment in the Double-Blind Withdrawal Period of the trial be stopped and the open-label portion of the study be continued, so as not to expose further subjects to placebo treatment. Amendment 4 to this protocol was based on that recommendation. The current amendment (Amendment 5) provides subjects who have completed one year in the study (Part 1) the opportunity to continue treatment for up to an additional 2 years or until they reach 18 years of age or until up to 3 months after the US FDA decision on the addition of pediatric data to the Xyrem US PI, whichever occurs first.

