## 7 STUDY ACTIVITIES

Study activities through the Double-Blind Treatment Period are presented by the following subject groups: subjects on Xyrem at study entry (Section 7.1) and Xyrem-naïve subjects (Section 7.2). PSG night activities are described in Section 7.3. Study activities for the Open-Label Safety Period for all subjects are described in Section 7.4. Study activities for Part 2 (Open-Label Continuation Period) are described in Section 7.5 for subjects continuing directly into Part 2 from Part 1 and in Section 7.6 for subjects re-enrolling in Part 2 after completing Part 1. Additional visits as required by local regulations may be conducted during the study.

The medical monitor may give permission for visits outside any particular visit window to accommodate necessary changes to complete a particular visit (e.g., travel issues, parental or family illness, etc.).

Subjects entering the Double-Blind Treatment Period after Amendment 4 becoming effective will receive open-label Xyrem treatment during this period. Subjects entering the Double-Blind Treatment Period before Amendment 4 becoming effective will continue to receive double-blind treatment during this period.

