## 9.8 Interim Analysis

A preplanned interim analysis was conducted after 35 subjects completed or discontinued early from the Double-Blind Treatment Period. The interim analysis was performed by a statistician not directly involved with the design and analysis of the study. The data were reviewed by a DSMB that recommended stopping placebo treatment in the Double-Blind Randomized-Withdrawal Period and continue the study as an open-label safety study because of positive efficacy results.

Considerations for stopping the study early included the following as initially planned. Given now the placebo treatment is stopped after the interim analysis review by DSMB, the DSMB will continue to review safety and PK data as outlined below.

Xyrem® (sodium oxybate) oral solution  
Clinical Study Protocol: 13-005 Amendment 5

Jazz Pharmaceuticals.

**For stopping the study early because of treatment success**, so that fewer subjects will be exposed to placebo: The O'Brien-Fleming approach will be used with the primary efficacy endpoint. This endpoint will be tested at a significance level of 0.005 at the interim analysis. If statistical significance is shown, the DSMB may recommend stopping the study considering the overall study objectives and subject's safety. If the study is not stopped, to maintain an overall alpha of 0.05, the final analysis will be conducted at a significance level of 0.048, based on one prior look at the data.

**For stopping the study early because of treatment failure:** In the interim analysis, if the null hypothesis for the primary efficacy endpoint is not rejected at the 0.005 significance level, then a futility analysis will be conducted. The conditional power approach will be used. Assuming the trend in the data observed up to the interim analysis will continue for the data collected between the interim analysis and the final analysis, the conditional power of rejecting the null hypothesis at the final analysis will be calculated. If the conditional power is less than 15%, it will be concluded that the study is unlikely to demonstrate efficacy and the DSMB may recommend stopping the study considering the overall study objectives and subject's safety. The study may be discontinued early due to futility.

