### **11.7 Protocol Adherence – Amendments**

The protocol must be read thoroughly and the instructions must be followed exactly.

Any changes in the protocol will require a formal amendment. Such amendments will be agreed upon and approved in writing by the Investigator and the Jazz Pharmaceuticals designees. The IRB/IEC will be notified of all amendments to the protocol. Amendments to the protocol will not be implemented until written IRB/IEC approval has been received.

If a country or region specific amendment is required based on local regulation, the amendment will be submitted to the IRB(s) and competent authority of that country or region only.

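### After the early efficacy stop, must the secondary tiers be tested below 0.05 because only the primary endpoint has a group-sequential boundary?

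*Protocol*

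**What the plan says.** Section 9.8 places the sequential boundary on the primary endpoint alone. "This endpoint will be tested at a significance level of 0.005 at the interim analysis", and had the study continued, "to maintain an overall alpha of 0.05, the final analysis will be conducted at a significance level of 0.048". The interim point is given as "A preplanned interim analysis was conducted after 35 subjects completed or discontinued early from the Double-Blind Treatment Period", out of the 70 that Section 9.2 planned for the randomized period.

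Section 9.6.1 states the overall aim as family-wise control at 0.05 with two-sided tests. It reports that the primary crossed at the interim and then fixes the level for what remains: "Tiered testing on secondary endpoints, as defined below, will be conducted with a significance level of 0.05, with all tests being two-sided". Each step down the list requires a favourable result. For Tier 2, for example: "If Xyrem is significantly better than placebo at this level, Tier 3 tests will be conducted". The synopsis repeats this. Neither place gives a secondary endpoint its own boundary.

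**The concern.** A fixed testing sequence lets each endpoint use the full alpha when there is one analysis. Here there were two possible analysis times, and the primary chose between them. Stopping on a high primary result also selects high values of any endpoint that correlates positively with it. Correlation is plausible for Tier 2, since the CGIc for cataplexy severity is rated over the same two weeks as the attack count. A null secondary tested at 0.05 on that selected data can show apparent benefit more than 2.5% of the time.

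The plan also lowers the primary's final level from 0.05 to 0.048 to remove an excess of similar order, and makes no matching adjustment for the secondaries. The claims at stake are Tier 2 and Tier 3. Tier 3, ESS (CHAD), carries the first secondary objective.

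**Working it through.** **Inputs.** From Section 9.8: primary levels 0.005 and 0.048, two-sided (z = 2.807 and 1.977), and an interim at 35 subjects. From Section 9.2: 70 planned, so the interim information is 35/70 = 0.5, with at least 80% power at two-sided 0.05. From Section 9.6.1: secondaries at 0.05 (z = 1.960). Not stated, so varied: the primary-secondary correlation (0 to 1), the true primary effect, and the number finally randomized.

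**1. The plan's own figures.** Overall two-sided error for the primary is 1 − P(|Z1| < 2.807, |Z2| < 1.977), with correlation √0.5 between looks. This gives 0.0499, which matches the stated 0.05. With 0.05 at the final look it would be 0.0519. The classical two-look O'Brien-Fleming levels are 0.0052 and 0.0480, so 0.005 and 0.048 are correct.

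**2. How many were randomized.** Thirty-five is the floor. "On February 24, 2016, the Data and Safety Monitoring Board (DSMB) for this study reviewed the results from a pre-planned interim analysis", and Amendment 4 is dated 5 April 2016, 41 days later. "Amendments to the protocol will not be implemented until written IRB/IEC approval has been received", and Section 7 says subjects who entered "before Amendment 4 becoming effective will continue to receive double-blind treatment during this period". Some overrun is therefore likely. Its size is not given, so I use 35, 42, 52–53, 63 and 70 subjects (information t = n/70 = 0.5, 0.6, 0.75, 0.9, 1.0).

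**3. Chance of a false claim of benefit on a null secondary.** This is P(primary crosses at the interim and the secondary at information t exceeds 1.960) + P(primary does not cross at the interim, crosses 1.977 at the final look, and the secondary there exceeds 1.960).

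The planned-power effect is 1.960 + 0.842 = 2.80 on the z scale at full information. Its interim stop probability is 1 − Φ(2.807 − 2.80 × 0.7071) = 0.204. Results at that effect, by numerical integration and confirmed with 4 million simulated trials:

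| Randomized | Correlation 0.3 | Correlations 0.5 to 1.0 |
|---|---|---|
| 35 | 0.0256 | 0.0283–0.0304 |
| 42 | 0.0250 | 0.0273–0.0292 |
| 52–53 | 0.0243 | 0.0261–0.0274 |
| 63 | 0.0239 | 0.0252–0.0259 |

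At 70 subjects, or at zero correlation, there is no excess over 0.025.

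**4. Larger primary effects.**
- Where the interim stop has 50% probability (drift 3.97), the rates for correlations 0.5 to 1.0 are 0.0252–0.0254 (63), 0.0253–0.0260 (52–53) and 0.0253–0.0274 (35).
- At 86% stop probability (drift 5.5), with correlations 0.5 to 0.99, they are 0.0250–0.0251, 0.0250–0.0252 and 0.0250–0.0254.

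**5. Worst case over all primary effects.** The maxima are 0.0263 (63), 0.0289 (52–53) and 0.0415 (35). The last needs correlation exactly 1.0 and a primary effect with only a 2.5% chance of stopping at the interim.

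**6. The rate the protocol states.** Counting both directions, the largest two-sided rates with 35 subjects, over primary effects up to about 4.8, are 0.0500, 0.0486, 0.0467, 0.0445 and 0.0459 at correlations 0, 0.3, 0.5, 0.7 and 1.0. Over the points tried, the maxima were 0.0496 at 52–53 subjects and 0.0499 at 63. The selection that raises the favourable tail lowers the unfavourable one by more, so the two-sided 0.05 holds.

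**7. Cost of forcing 0.025 in the benefit direction.** Holding it for every correlation up to 1.0 and every primary effect needs 0.029 (35), 0.037 (42), 0.043 (52–53) or 0.0475 (63). A secondary with 80% power at 0.05 has power Φ(2.80 − z) at the lower level: 73.2%, 76.3%, 78.2% and 79.4%. The largest loss is 80 − 73.2 = 6.8 points. If protection is needed only for correlations up to 0.7, about 0.040 (35), 0.046 (52–53) and 0.0486 (63) suffice.

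**The case for a change.** The best case for a change is that the protocol itself fixes 0.05 tier by tier, so this is not detail left to the SAP. Progress down the list requires benefit, so the favourable tail is the error that matters in practice. Between 35 and 53 subjects, the excess on a well-correlated secondary can equal or exceed what the 0.048 removes for the primary: 0.0519/2 is about 0.0259 in the benefit direction, against 0.0261–0.0304 at the planned-power effect. A lower level could only make the sponsor's test stricter.

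The mechanism and the numbers stand. Three things weaken the conclusion.

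- The 0.025 limit is inferred from the condition for moving to the next tier. The protocol's stated standard is two-sided, and it is met.
- The parallel with the primary is loose. The 0.048 pays for two tests of the same endpoint, whereas each secondary is tested once and is affected only through its correlation with the stopping decision.
- The no-stop path is modelled at 0.05, but Section 9.8 can be read as putting the whole final analysis at 0.048. On that reading, at planned power and 63 subjects, the rates are 0.0233, 0.0246, 0.0253 and 0.0257 at correlations 0.3, 0.5, 0.7 and 0.99, so the excess at 0.5 disappears. With fewer subjects it shrinks but remains.

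**Conclusion.** No change to the plan is needed. The boundary does cover the primary alone, and the benefit-direction rate on a correlated null secondary can slightly exceed 0.025. At the planned-power effect and correlations of 0.5 to 1.0, the excess is under 0.001 at 63 randomized and about 0.003 to 0.005 at 35. It nearly vanishes when the primary effect makes an interim stop likely. The two-sided family-wise 0.05, the only rate the protocol promises, is kept.

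Tightening the levels is a trade-off rather than a correction. The levels that guarantee 0.025 protect against a secondary that is perfectly correlated with the primary yet has no effect of its own. They depend on a number randomized that the protocol does not give. They are not unique: a Pocock-type boundary for the secondaries (0.0294 at each look) or the primary's own levels would also work, with worst cases of 0.0249 and 0.0250. They cost power and would be set once the primary result was known. The missing count of randomized subjects is a gap in detail, not an error.

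This rests on jointly normal test statistics, a constant correlation, information proportional to the number randomized, and a trial that continued to 70 if not stopped.

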## 9.7 Statistical Analysis of Pharmacokinetic Variables

**To address Secondary Objective 2:** Concentration data for sodium oxybate will be summarized by sampling time point and by PK parameter using descriptive statistics for each age group and overall. Dose proportionality will be assessed from the ratio of AUC and  $C_{max}$  values. The ratios and their 90% confidence intervals will be presented. If warranted, regression models will be used to explore the relationship between plasma concentration and dose on a mg/kg basis.

## 9.8 Interim Analysis

A preplanned interim analysis was conducted after 35 subjects completed or discontinued early from the Double-Blind Treatment Period. The interim analysis was performed by a statistician not directly involved with the design and analysis of the study. The data were reviewed by a DSMB that recommended stopping placebo treatment in the Double-Blind Randomized-Withdrawal Period and continue the study as an open-label safety study because of positive efficacy results.

Considerations for stopping the study early included the following as initially planned. Given now the placebo treatment is stopped after the interim analysis review by DSMB, the DSMB will continue to review safety and PK data as outlined below.

Xyrem® (sodium oxybate) oral solution  
Clinical Study Protocol: 13-005 Amendment 5

Jazz Pharmaceuticals.

**For stopping the study early because of treatment success**, so that fewer subjects will be exposed to placebo: The O'Brien-Fleming approach will be used with the primary efficacy endpoint. This endpoint will be tested at a significance level of 0.005 at the interim analysis. If statistical significance is shown, the DSMB may recommend stopping the study considering the overall study objectives and subject's safety. If the study is not stopped, to maintain an overall alpha of 0.05, the final analysis will be conducted at a significance level of 0.048, based on one prior look at the data.

**For stopping the study early because of treatment failure:** In the interim analysis, if the null hypothesis for the primary efficacy endpoint is not rejected at the 0.005 significance level, then a futility analysis will be conducted. The conditional power approach will be used. Assuming the trend in the data observed up to the interim analysis will continue for the data collected between the interim analysis and the final analysis, the conditional power of rejecting the null hypothesis at the final analysis will be calculated. If the conditional power is less than 15%, it will be concluded that the study is unlikely to demonstrate efficacy and the DSMB may recommend stopping the study considering the overall study objectives and subject's safety. The study may be discontinued early due to futility.

**For stopping the study early because of safety reasons:** Safety data, including the incidence of adverse events, will be reviewed by the DSMB at regular intervals. Any serious adverse events or deaths will be given detailed attention. Taking all data reviewed into account, the DSMB will determine if the risk to subjects warrants study discontinuation.

An ongoing analysis of the PK data will also be conducted to determine if a sufficient number of samples have been collected to adequately characterize the PK of Xyrem in children and adolescents.

## 9.9 Safety Analysis

Safety will be assessed at time points specified in the schedules of events, as well as throughout the study. Safety assessments will include the following:

- Adverse event (AE) monitoring
- Vital signs
- Physical examinations (including weight and height)
- 12-lead ECG
- PSG parameters (including respiratory measures)
- Clinical laboratory tests (chemistry, hematology, and urinalysis)
- Assessments of growth and precocious puberty
- C-SSRS (Children's Since Last Visit version for subjects under 12 years of age and the Since Last Visit version for subjects 12 years of age and older) for emergent suicidality
- CDI 2:SR[S] for emergent or worsening depression
- MASC-10 for emergent or worsening anxiety
- Serum pregnancy tests (if applicable)

Xyrem® (sodium oxybate) oral solution  
Clinical Study Protocol: 13-005 Amendment 5

Jazz Pharmaceuticals.

Exploratory endpoint:

- CO2 monitoring (EtCO2 or TcCO2) in sites where monitoring is routinely performed and performance will not negatively impact study participation or PSG data integrity

A DSMB will review the safety data on a regular basis, including monitoring for the following AEs:

- Confusion
- Somnolence and more pronounced levels of depressed consciousness
- Respiratory depression
- Depressed mood and suicidality
- Anxiety
- Sleepwalking and other parasomnias
- Abuse and misuse of study drug
- Weight loss

Adverse events will be mapped to system organ classes and preferred terms using the Medical Dictionary for Regulatory Activities (MedDRA).

**To address Primary Objective 2 and Secondary Objective 3:** Safety will be summarized using descriptive statistics and reported separately for Part 1 and Part 2 as well as across the entire study (Part 1 and Part 2) for select analyses. Adverse events will be assessed for subpopulations including Xyrem naïve, subjects on Xyrem at study entry, Ages 7-11, and Ages 12-17, as applicable. When summarizing data across the entire study by subpopulations, subjects are analyzed according to their initial enrollment status. For Part 1, adverse events will also be summarized by treatment group and by dose. Safety analyses will also include an analysis of the nadir oxygen saturation level at each dose, and number and duration of any confirmed desaturations below 90%, 80%, 70%, 60% and 50% on PSG nights excluding the screening PSG. For Part 2, safety data will be summarized by Ages 7-11, Ages 12-17, and overall.

